### **3. PRELIMINARY RESULTS:**

Our preliminary results are shown in the work entitled “**Low zinc levels at clinical admission associates with poor outcomes in COVID-19**” (13) which is the result of a tight collaboration between the laboratory of [name] (Hospital del Mar) and those of [name] and [name] (both at DCEXS, UPF).

This work aimed to focus clinical attention on serum zinc content (SZC) in COVID-19 patients. Our analysis showed a robust correlation between low SZC with COVID-19

severity and mortality. The cause is likely to be a combination of immune system imbalance and a direct benefit of viral replication.

A summary of the results obtained:

- In our retrospective observational study with 249 COVID-19 patients, **23% of the patients had at admission SZC lower than 50µg/dl**, the cutoff associated with ZD and development of clinical signs.
- Our study showed that **low SZC correlates with higher IL-6 and C-reactive protein at admission**, higher peak IL-6 during the episode.
- We detected in the low SZC group that subjects needed higher time to recover (25 days) versus the control group (8 days). In the same direction, the **mortality in low SZC patients was higher (21%) than in the control group (5%)** with normal zinc concentration.
- **SARS-CoV2** Infections in cell culture demonstrated that **low zinc levels favors SARS-CoV2 viral expansion** in the infected cells.

These results highlighted the urgent need to start clinical trials supplementing with zinc low SZC patients at admission to reestablish zinc homeostasis in order to study the cause-effect association between zinc nutritional status and COVID-19 progression. We expect with this new project that zinc supplementation in low SZC COVID-19 patients will

balance what has been called the cytokine storm caused by SARS-CoV-2 and as a consequence will reduce COVID-19 severity and mortality.

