### **1) Clinical trial objectives**

#### **Primary objective**

To evaluate the effectiveness of oral zinc supplementation (83.91 mg zinc acetate) Zinc+NM QD (80mg Zn2+) QD as compared to placebo as compared to control group without zinc supplementation to reduce IL-6 increase in the course of SARS-CoV-2 infection, to decrease days to clinical recovery and to decrease the percentage of people with COVID-19 who have disease progression by Week 2, defined as inpatients, worsening of  $\geq 1$  level on the WHO 9-point ordinal scale

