### **Study Endpoints**

#### **Primary Endpoints**

- Number of days since admissions to clinical recovery
- Change in IL-6 levels from baseline to Week 2.
- Percentage of patients with disease progression by Week 2 based on WHO 9-point ordinal scale

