### **Task 1.1.1 Visits and sample collection**

1.- Visit 1. Screening. Randomization. Baseline. Phase / Visit 0 or 1 ( Day 1 or up to 1 day  
Prior to Baseline/Randomization; In Person)

Visit performed at admission (+1). Written informed consent obtained. Medical history.  
Vital signs assignment. Clinical labs (CBC, CMP, CRP, ferritin, D-dimer,IL-6, zinc)

2.-Visit 2 / Week 1 (Day 7  $\pm$  2 days)

A complete record of AEs and concomitant therapies will be taken into account. 3.-

Visit 3 / Week 2 (Day 14  $\pm$  2 days), End of Treatment

A complete vital sign assessment (sitting blood pressure, heart rate, respiratory rate, O2  
sat, and oral temperature) review and record AEs and concomitant therapies, clinical  
labs (stated above) and PBMCs. Collect blood samples for future studies.

4.-Visit 4 / End of Study (Day 28  $\pm$  4 days)

Clinical labs (stated above) and PBMCs. Collect blood samples for future studies.

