### **Statistical analysis**

**Randomization: Subjects** will be randomized in a 1:1 ratio to:

- 83.91 mg zinc acetate (Zinc+NM) QD + standard of care for 2 weeks
- Standard of care for 2 weeks

**Determination of sample Size:** Sample size calculations are aimed at comparisons of days to clinical recovery between zinc supplementation and standard of care alone. Assuming alpha = 0.05 and a 10% dropout rate, randomization of 60 subjects will

provide 80% power to detect a difference in time to recovery between arms of 3 days assuming a SD of 4 days. This sample size will also provide at least 80% power to detect a change in percentage of people with clinical progression of 5% based on an estimated

clinical progression rate of 20% in the standard of care arm.

**Analysis Populations:** The analysis population for efficacy will be per protocol which includes all randomized subjects who complete 2 weeks of therapy and/or return for Week 2 visit. All safety analyses will include all randomized subjects who are

administrated at least 1 packet of the investigational product.

**Baseline Characteristics:** Demographics and Baseline characteristics will be summarized descriptively by group and overall using per protocol population. The following Baseline

characteristics will be summarized: sex, race, age, comorbidities, ethnicity

**Clinical Laboratory Assessments:** Blood chemistry, hematology parameters will be summarized at Baseline as well as visit 3 and 4. Laboratory values at Baseline and subsequent changes in laboratory values will be summarized descriptively overall and

by therapy group.

**Vital signs:** Vital sign measurements will be summarized at Baseline, Week 2 and Week 4. In addition, changes from Baseline to Week 2 or 4 will be summarized. For each summary the number, mean, median, standard deviation, minimum, and maximum

values will be presented overall and by therapy group.

**Safety Analyses:** All safety analyses will be based on the Safety Population, comprising all subjects who are randomized to the therapy group and subsequently receive at least one packet of investigational product. Safety assessments will be analyzed by frequency of events/abnormalities for categorical values or summarized using descriptive statistics

(mean, standard deviation, median, range, and number of observations).

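### The IL-6 primary endpoint has no stated scale, model or baseline adjustment, and an unadjusted raw change could lose from little to most of the power of a log-scale analysis of the same samples

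*Combined protocol and SAP*

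**What the plan says.** Under Study Endpoints, one of the three primary endpoints is "Change in IL-6 levels from baseline to Week 2". The Primary objective gives the direction: zinc is meant "to reduce IL-6 increase in the course of SARS-CoV-2 infection". Task 1.1.2 (Assessment of Efficacy) lists IL-6 levels as an outcome and adds nothing on how they are compared.

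In the Statistical analysis section, the only text that reaches IL-6 is the general paragraph on clinical laboratory assessments, where "subsequent changes in laboratory values will be summarized descriptively". No section names a transformation, a test, a model or a baseline covariate for IL-6. The sample size does not rest on IL-6 either: "Sample size calculations are aimed at comparisons of days to clinical recovery between zinc supplementation and standard of care alone", with a second statement about clinical progression.

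The samples exist. The baseline visit in Task 1.1.1 includes "Clinical labs (CBC, CMP, CRP, ferritin, D-dimer,IL-6, zinc", and the same laboratory panel is repeated at Week 2 and Day 28.

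**The concern.** A change in levels is ordinarily computed as Week 2 minus baseline, in concentration units. IL-6 is a positive marker, and the protocol expects zinc to "balance what has been called the cytokine storm caused by SARS-CoV-2". It enrols adults with COVID-19 without an IL-6 limit or an upper severity limit other than a life expectancy under 72 hours. A long upper tail is therefore plausible, although the documents do not show one. With such a tail, an unadjusted comparison of raw changes has two weaknesses. It keeps all the variance of the admission values, and a few patients supply much of the spread.

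At stake is whether one of three primary endpoints can show a real effect. The Limitation paragraph says that finding no benefit would mean low zinc is a consequence of inflammation, and an insensitive IL-6 comparison would feed that conclusion. Because the trial is open-label and the scale is open, the scale could also be chosen after the data are seen.

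**Working it through.** **Inputs from the protocol.** 60 randomized 1:1, 10% dropout, so 60 × 0.9 / 2 = 27 evaluable per arm; alpha 0.05, taken as two-sided.

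**The plan's own power figure.** For recovery time (3 days, SD 4): 3 / (4 × √(2/27)) = 3 / 1.089 = 2.756, and Φ(2.756 − 1.960) = 0.787. This agrees with the stated 80%. No power is stated for IL-6, so there is no IL-6 figure to reproduce.

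**Assumed IL-6 inputs.** Log-normal values; the same log-SD *s* at both visits, 0.8 to 1.5; admission/Week-2 correlation on the log scale ρ = 0.3; true zinc/control ratio at Week 2 *r* = 0.4; control Week-2 level equal to *k* times the admission level, with *k* from 0.25 (falling) through 1 (flat) to 2 (doubling).

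**Log scale, s = 1.0.** The effect is |ln 0.4| = 0.916, and √(2/27) = 0.272.
- Log change: SD = s√(2(1 − ρ)) = 1.183; 0.916 / (1.183 × 0.272) = 2.85; Φ(2.85 − 1.96) ≈ 0.81. Simulated: 78–80%.
- Log ANCOVA: SD = s√(1 − ρ²) = 0.954; 0.916 / (0.954 × 0.272) = 3.53; Φ(3.53 − 1.96) ≈ 0.94. Simulated: 92–93%.

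Neither depends on *k*.

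**Raw change, s = 1.0, in units of the admission geometric mean.** The between-arm difference is k(1 − r)e^(s²/2). The variance of change in an arm with Week-2 level *m* is V(1 + m²) − 2mC. Here V = e^(s²)(e^(s²) − 1) = 4.671, C = e^(s²)(e^(ρs²) − 1) = 0.951, and m = k in controls and rk on zinc.

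| k | Difference | Variance, control / zinc | SE | Normal approximation | Simulated power |
|---|---|---|---|---|---|
| 0.25 | 0.247 | 4.49 / 4.53 | 0.578 | 6% | 7% |
| 1 | 0.989 | 7.44 / 4.66 | 0.669 | 32% | 38% |
| 2 | 1.978 | 19.55 / 6.14 | 0.976 | 53% | about 65% |

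The signal shrinks with the Week-2 level while the admission variance V stays. That is why a falling IL-6 hurts the raw change most. The approximation is rough for skewed data, so the simulated column is the one to use.

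**Simulated power across log-SD** (t-tests and ANCOVA; at 1,500 runs per cell, Monte Carlo error is up to about 2.5 points):

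| Log-SD | Raw vs log change, flat or falling | Raw vs log change, doubling | Raw vs log ANCOVA |
|---|---|---|---|
| 0.8 | 61% vs 93% (flat) | 87% vs 93% | 95% vs 99% |
| 1.0 | 7–38% vs 78% | 65% vs 80% | 76% vs 92% |
| 1.25 | 5–24% vs 58–61% | 38% vs 60% | 49% vs 78% |
| 1.5 | 5–14% vs 46–49% | 22% vs 47% | 30% vs 63% |

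Relative loss from raw change at log-SD 1.0: (78 − 7)/78 = 91% at *k* = 0.25, (78 − 38)/78 = 51% if flat, and (80 − 65)/80 = 19% if doubling. Type I error under the null was 3.6–5.7%.

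**Splitting the gap (flat IL-6).** At log-SD 1.0, adding the baseline covariate moves power from 38% to 76% (38 points), and the log scale then takes it to 92% (16 points). At log-SD 1.5 the steps are 14% to 30% (16 points) and 30% to 63% (33 points).

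**A milder effect (r = 0.5, ρ = 0.5).** Raw against log change at log-SD 1.0 is 13% vs 70% if IL-6 halves, 34% vs 71% if flat and 53% vs 70% if it doubles. At log-SD 0.5 with flat IL-6 it is 95% vs 100%. Across these runs, the three most extreme of 54 patients carry about 40% of the squared variation in raw change at log-SD 0.5, 60% at 1.0 and 80% at 1.6.

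**The case against.** The strongest reply is that the protocol never says the difference is absolute, and that every IL-6 input above is assumed. That stands. The documents report only qualitative relations, such as "low SZC correlates with higher IL-6 and C-reactive protein at admission", with no mean, SD or target effect. No power was promised for IL-6, so these figures compare analyses and do not show a shortfall against a stated power.

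A reader might infer that the endpoint is fixed as a raw difference, that a few very high admission values dominate it, and that most of the power is lost. The documents do not support this. The objective speaks of reducing an increase, so a rise is a natural scenario. If IL-6 doubles, the raw change correlates only about −0.2 to −0.46 with the admission value, against −0.66 to −0.97 when IL-6 is flat or falling. Week-2 values then contribute much of the spread. The loss under doubling is below half up to log-SD 1.25 and about half at 1.5.

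Two further replies have partial force. Baseline adjustment on the raw scale closes much of the gap at log-SD 1.0 or below, though not at higher values. A rank test on raw change is less exposed to extremes: with r = 0.5, ρ = 0.5 and log-SD 1.0, it matches log change when IL-6 doubles (69% vs 70%). It falls behind when IL-6 is flat (49% vs 71%) or halves (24% vs 70%).

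Finally, a proportional effect favours logs, and an additive effect was not simulated.

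**Conclusion.** The point holds in a bounded form. A primary endpoint has no stated scale, model or baseline adjustment, and its plain wording leads to an unadjusted raw difference. If IL-6 is right-skewed and the zinc effect is proportional, that analysis loses between little (87% vs 93% at log-SD 0.8 with doubling) and most (7% vs 78% at log-SD 1.0 with IL-6 falling to a quarter) of the power of a log-change analysis. Where in that range the trial would fall depends on the log-SD and the Week-2 trend, which the documents do not give.

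The loss has two sources, missing baseline adjustment and scale, and should not be credited to scale alone. Adjusting on both scales leaves a scale effect of 4 points at log-SD 0.8, rising to 33 points at 1.5. Log ANCOVA was at least as good as every raw-scale option in every scenario examined. This should be corrected before analysis; confidence in the size is moderate because all IL-6 inputs are assumed.

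**What to change.** In the Statistical analysis section, state the primary IL-6 analysis as a linear model for log(IL-6) at Week 2 with treatment arm and log(admission IL-6) as covariate. Report the between-arm ratio of geometric means with its 95% CI. Set values below the assay limit to one value stated in advance. Align the endpoint wording with this, so that change is read as a ratio adjusted for admission level.

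The cost is wording only: the baseline and Week-2 samples are already scheduled. The downside is that the result is read as a percentage difference and not in concentration units.

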#### **Secondary Endpoints**

- Change in Covid-19 signs/symptoms: dyspnea, diarrhea, temperature, neutrophil count... at Week 2

#### **Safety Endpoints**

- Incidence of AEs and serious adverse events

### **Study Design**

This is a randomized, open-label clinical study evaluating the effectiveness of zinc supplementation as compared to standard of care on need disease severity and on IL-6

levels in people with COVID-19. Subject eligibility will be based on inclusion and exclusion criteria

**Population of study:** Sixty eligible adult subjects at one clinical site in Spain (Hospital del Mar) will be randomized in a 1:1 ratio to:

- ~~Zinc acetate 80mg QD~~ 83.91 mg zinc acetate (Zinc+NM) QD + standard of care for 2 weeks
- Standard of care for 2 weeks

**Study phases (4 weeks):**

- Screening + Randomization + Baseline Visit (Visit 1, same day as or up to 1 day before Baseline Visit)
- Treatment (Day 1 to Day 14) Starting on Day 1 (Baseline/Randomization), Randomized subjects will receive 80mg zinc for 2 weeks. Day 7 for clinical state. Day 14 follow up visit.
- Follow up phase : Day 28 for clinical state.

**Inclusion Criteria**

To be eligible to participate in this study, all of the following criteria must apply:

- Subject is  $\geq 18$  years of age.

- Male or female.
- Subject with diagnosis of COVID-19 based on + RNA or IgM test or compatible clinical presentation.
- Ability to take oral zinc supplementation.
- Subject or surrogate decision maker is capable of understanding and willing to sign the informed consent form.

**Exclusion Criteria** and withdrawals are detailed in the document sent to the Ethics Committee.

Subjects are not permitted to enroll in the study if any of the following criteria apply:

- Female subjects who are pregnant
- Female subjects who are breast-feeding.
- Difficulty or inability to take oral medication.
- Subject is enrolled in another randomized clinical trial in the last 3 months.
- Life expectancy less than 72 hours at hospital admission.
- Conditions that in the opinion of the investigator may interfere with the subject's ability to comply with this protocol (e.g drug abuse, psychiatric disorders).

### **Task 1.1.1 Visits and sample collection**

1.- Visit 1. Screening. Randomization. Baseline. Phase / Visit 0 or 1 ( Day 1 or up to 1 day  
Prior to Baseline/Randomization; In Person)

Visit performed at admission (+1). Written informed consent obtained. Medical history.  
Vital signs assignment. Clinical labs (CBC, CMP, CRP, ferritin, D-dimer,IL-6, zinc)

2.-Visit 2 / Week 1 (Day 7  $\pm$  2 days)

A complete record of AEs and concomitant therapies will be taken into account. 3.-

Visit 3 / Week 2 (Day 14  $\pm$  2 days), End of Treatment

A complete vital sign assessment (sitting blood pressure, heart rate, respiratory rate, O2  
sat, and oral temperature) review and record AEs and concomitant therapies, clinical  
labs (stated above) and PBMCs. Collect blood samples for future studies.

4.-Visit 4 / End of Study (Day 28  $\pm$  4 days)

Clinical labs (stated above) and PBMCs. Collect blood samples for future studies.

### **Task 1.1.2 Assessment of Efficacy**

#### **Outcomes measured.**

- Clinical recovery
  - Defined: Sat O2 (0.21) >94% or to baseline Sat O2 in case of chronic respiratory

- Temperature <37C
  - Heart Rate <90 bpm & Systolic blood pressure >100
  - Oral tolerance
  - Baseline consciousness
- 
- Assessment of Covid-19 Disease Severity as per the WHO 9-point ordinal scale  
Ordinal scale, 9 points
  - IL-6 levels

**EO:** We expect to prove the effectiveness of zinc supplementation to reduce COVID-19 severity and mortality

**D1:** Guideline for zinc-based nutritional supplementation to treat COVID-19 patients admitted in hospitals

### **Statistical analysis**

**Randomization: Subjects** will be randomized in a 1:1 ratio to:

- 83.91 mg zinc acetate (Zinc+NM) QD + standard of care for 2 weeks
- Standard of care for 2 weeks

**Determination of sample Size:** Sample size calculations are aimed at comparisons of days to clinical recovery between zinc supplementation and standard of care alone. Assuming alpha = 0.05 and a 10% dropout rate, randomization of 60 subjects will

provide 80% power to detect a difference in time to recovery between arms of 3 days assuming a SD of 4 days. This sample size will also provide at least 80% power to detect a change in percentage of people with clinical progression of 5% based on an estimated

clinical progression rate of 20% in the standard of care arm.

**Analysis Populations:** The analysis population for efficacy will be per protocol which includes all randomized subjects who complete 2 weeks of therapy and/or return for Week 2 visit. All safety analyses will include all randomized subjects who are

administrated at least 1 packet of the investigational product.

**Baseline Characteristics:** Demographics and Baseline characteristics will be summarized descriptively by group and overall using per protocol population. The following Baseline

characteristics will be summarized: sex, race, age, comorbidities, ethnicity

**Clinical Laboratory Assessments:** Blood chemistry, hematology parameters will be summarized at Baseline as well as visit 3 and 4. Laboratory values at Baseline and subsequent changes in laboratory values will be summarized descriptively overall and

by therapy group.

**Vital signs:** Vital sign measurements will be summarized at Baseline, Week 2 and Week 4. In addition, changes from Baseline to Week 2 or 4 will be summarized. For each summary the number, mean, median, standard deviation, minimum, and maximum

values will be presented overall and by therapy group.

**Safety Analyses:** All safety analyses will be based on the Safety Population, comprising all subjects who are randomized to the therapy group and subsequently receive at least one packet of investigational product. Safety assessments will be analyzed by frequency of events/abnormalities for categorical values or summarized using descriptive statistics

(mean, standard deviation, median, range, and number of observations).

**Adverse events:** Adverse events will be coded using the Medical Dictionary for Regulatory Activities (MedDRA) coding dictionary. Adverse events will be defined as any event with a start date occurring on or after initiation of therapy on Day 1 or, if pre-existing, worsening after initiation of therapy on Day 1. The incidence of AEs will be

summarized by body system and MedDRA preferred term, overall and by therapy group.

If a subject reports the same AE more than once, then that subject will only be counted once for the summary of that AE, using the most severe intensity.

**Handling of Dropouts or Missing Data :** Dropouts or participants missing data for the primary endpoints will be excluded from the analysis.

**Limitation:** We might find no benefit in COVID-19 patients supplemented with zinc. That would mean that the low zinc levels detected in COVID-19 patients with worse prognosis are a consequence of the inflammatory status. The results will be also very helpful for physicians worldwide.

- **To study the immune responses of the COVID-19 patients enrolled in the clinical trial (Subproject 2)**

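### Days to clinical recovery has no stated analysis model, severity covariate or stratification factor, although starting severity is probably prognostic and can be had at entry

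*Combined protocol and SAP*

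**What the plan says.** The Statistical analysis section sizes the trial on one endpoint: "Sample size calculations are aimed at comparisons of days to clinical recovery between zinc supplementation and standard of care alone". The design is said to "provide 80% power to detect a difference in time to recovery between arms of 3 days assuming a SD of 4 days", and the other inputs are an alpha of 0.05, 60 patients randomised and 10% dropout. No covariate, correlation or explained variance is given, and the text does not say whether the SD is raw or residual.

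On allocation, the plan says only that subjects "will be randomized in a 1:1 ratio to" the two arms. No stratification factor appears there or under Study Design. The rest of the section covers analysis populations, descriptive summaries, safety and the exclusion of missing data. It names no test or model for any of the three primary endpoints.

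Severity information appears in several places:

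- **Entry criteria.** The diagnostic criterion is "Subject with diagnosis of COVID-19 based on + RNA or IgM test or compatible clinical presentation". No severity range is set in the printed list.
- **Outcome definition.** Task 1.1.2 defines clinical recovery by thresholds for oxygen saturation, temperature, heart rate and systolic pressure, plus oral tolerance and baseline consciousness. It also lists "Assessment of Covid-19 Disease Severity as per the WHO 9-point ordinal scale".
- **Visit 1 (Task 1.1.1).** Vital signs and laboratory tests are taken. Oxygen saturation is itemised among the vital signs only at Visit 3. No WHO assessment is listed at Visit 1, but the primary objective defines progression as worsening by at least one level, which requires a starting level.
- **Baseline summaries.** The listed "characteristics will be summarized: sex, race, age, comorbidities, ethnicity". Separately, "Vital sign measurements will be summarized at Baseline, Week 2 and Week 4", with results by therapy group.

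**The concern.** A patient who enters close to the recovery thresholds should usually reach them sooner than one who enters far from them. Severity at entry is therefore a likely source of between-patient variation in days to recovery, and the entry criteria leave room for it to vary.

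Two things are at stake. The first is precision: if severity stays in the error term, power that a prognostic covariate could supply is forgone. The second is chance imbalance. With about 30 patients per arm and no stratification, the arms may differ in starting severity, and without adjustment that difference carries into the estimated zinc effect.

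The trial is also open-label. If the model and covariates are chosen after outcome data have been seen, the choice can be influenced by the result, so they should be fixed in advance.

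**Working it through.** **Inputs from the plan.** 60 randomised 1:1, 10% dropout, difference 3 days, SD 4 days, alpha 0.05. Evaluable: 60 × 0.9 = 54, or 27 per arm. *Assumptions:* a two-sided test, because sidedness is not stated (one-sided 0.05 gives 86.7%, which does not match 80%), and a comparison of means.

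**Step 1. Reproduce the stated power.**
SE of the difference = 4 × √(2/27) = 1.089 days. Difference/SE = 3/1.089 = 2.756.
- Normal approximation: Φ(2.756 − 1.960) = Φ(0.796) = 78.7%.
- Noncentral t, 52 degrees of freedom: 77.2%.
- For comparison, 30 per arm with no dropout: 82.8% by the normal approximation.

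The stated 80% is thus close to what an unadjusted comparison of means gives, with no covariate needed to reach it.

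**Step 2. Add a severity covariate, linear model.**
Take 4 days as the raw SD and let rho be the correlation (multiple correlation if two covariates) between baseline severity and days to recovery. Residual SD = 4 × √(1 − rho²). Power is by noncentral t at 27 per arm, with one degree of freedom spent:

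| rho (assumed) | Residual SD | Difference/SE | Power | Gain over 77.2% |
|---|---|---|---|---|
| 0.2 | 3.92 | 2.81 | 78.8% | 1.6 points |
| 0.3 | 3.82 | 2.89 | 80.9% | 3.7 points |
| 0.4 | 3.67 | 3.01 | 83.9% | 6.7 points |
| 0.5 | 3.46 | 3.18 | 87.7% | 10.6 points |
| 0.6 | 3.20 | 3.44 | 92.2% | 15.0 points |

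Spending a second degree of freedom changes none of these by as much as 0.1 point. A gain of 5 points needs rho of about 0.35.

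**Step 3. Cost if the covariates are useless.**
With rho = 0 and two degrees of freedom spent, power goes from 77.17% to 77.11%, a loss of 0.06 point.

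**Step 4. Size of chance imbalance.**
If the arms differ in standardised baseline severity by k standard errors, the unadjusted difference shifts by k × rho × 4 × √(2/27) days.
- rho = 0.5: 0.54 days at k = 1 and 1.07 days at k = 1.96.
- rho = 0.3: 0.33 days at k = 1 and 0.64 days at k = 1.96.

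The target difference is 3 days, so the larger shift at rho 0.5 is 1.07/3 = 36% of it.

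As a second view, suppose some of the 60 patients form a more severe group, allocated 30:30 without stratification. The hypergeometric chance that the arms differ by at least 20 percentage points in that group is 10% for 12 such patients, 16% for 18 and 20% for 30. The group sizes and the 20-point threshold are assumptions.

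**The case against.** The strongest reply is that the plan makes no choice to leave severity out. It names no analysis method at all, and the sample-size sentence does not mention adjustment. A reader might infer that an unadjusted test has been specified; the documents do not support that. This part of the objection stands: the more basic gap is the missing primary model, and the severity covariate belongs in the remedy for it.

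A reader might also infer that about ten points of power are being lost. That does not hold either. The figure needs rho near 0.5, which appears nowhere in the documents, and the stated design already delivers roughly its stated power. What is at issue is a gain forgone. If 4 days was meant as a residual SD, there is no gain beyond the stated power.

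A third inference is that severity imbalance would go unseen. Baseline vital signs are to be summarised by therapy group, so imbalance in those would show. Only WHO level is missing from the planned baseline summaries.

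Other points stand in part. Baseline oxygen saturation is inferred from Visit 1 vital signs and WHO level from the definition of progression; neither is itemised at that visit. Saturation measured on oxygen may rank severity poorly unless the support is recorded, since recovery is judged at an inspired fraction of 0.21. Patients are inpatients able to take oral treatment, those with life expectancy under 72 hours are excluded, and the plan refers to a separate ethics document for its exclusions. The spread of severity may therefore be narrower than the printed criteria allow. Finally, chance imbalance under randomisation is not bias, and the unadjusted standard error already allows for it. Adjustment still gives a more precise estimate and one corrected for the imbalance that actually occurred.

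**Conclusion.** The point holds as a recommended improvement. For the endpoint that sizes the trial, no model, severity covariate or stratification factor is stated, and the sample size reproduces as an unadjusted comparison (77.2% by t, 78.7% by normal approximation). Starting severity is likely to be prognostic and is obtainable at entry, partly by inference.

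The benefit is a range: about 4, 7, 11 and 15 points of power at rho 0.3, 0.4, 0.5 and 0.6, and under 2 points at rho 0.2. It rests on an assumed rho, a two-sided test, 27 evaluable patients per arm, a raw SD of 4 days, and a linear model on fully observed days. Deaths and patients not recovered by Day 28 would call for another method. The gain is not quantified for a Cox model or for an adjusted risk difference.

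Nothing here shows that the trial falls materially short of its stated power for this endpoint or that its randomised comparison is invalid.

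**What to change.** In the Statistical analysis section:

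1. Name the primary model for days to clinical recovery, with treatment arm, baseline WHO level and baseline oxygen saturation as prespecified covariates. Use a linear model, or a Cox model if the endpoint is analysed as time to event.
2. Keep the unadjusted comparison as a sensitivity analysis.
3. Adjust the comparison of progression by Week 2 for baseline WHO level, for example as an adjusted risk difference.
4. Add WHO level to the listed baseline characteristics. Vital signs are already summarised by arm.
5. State whether the SD of 4 days is raw or residual. Present any power gain as a range with its assumed correlation.

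In Task 1.1.1, list WHO level and oxygen saturation explicitly at Visit 1, with oxygen support at the time of measurement.

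**Cost.** Plan wording and two explicit Visit 1 entries, with no additional patients or visits. The WHO level is needed for the progression endpoint in any case. With each covariate entered as a single term, two degrees of freedom are spent, which costs under 0.1 point of power if neither is prognostic.

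### The 4-day SD behind the 80% power for time to recovery has no source and does not fit the sponsor's own cohort if the trial enrols a similar zinc mix

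*Combined protocol and SAP*

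**What the plan says.** Under Statistical analysis, Determination of sample Size, the plan aims the sample size at the comparison of days to clinical recovery. With alpha at 0.05 and one patient in ten expected to drop out, a trial of 60 is said to "provide 80% power to detect a difference in time to recovery between arms of 3 days assuming a SD of 4 days". Allocation is 1:1. Neither the source of the SD nor the sidedness of the test is given. Under Handling of Dropouts or Missing Data, "Dropouts or participants missing data for the primary endpoints will be excluded from the analysis", so the power rests on the patients left after dropout.

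Section 3, Preliminary Results, describes the sponsor's retrospective cohort of 249 COVID-19 patients. At admission 23% had serum zinc below 50 µg/dl. In the low-zinc group, "subjects needed higher time to recover (25 days) versus the control group (8 days" days being the only summary given. No SD is reported, and the text does not say whether these are means or medians.

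The Inclusion and Exclusion Criteria list no serum-zinc threshold, although they refer to further exclusion details in a document held by the Ethics Committee. Zinc is among the laboratory tests at Visit 1 (Task 1.1.1). The plan mentions no stratification or adjustment for it.

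**The concern.** An SD of 4 days is a statement about how much recovery times vary among the patients compared. The cohort describes two groups whose typical recovery times differ by 17 days, with nearly a quarter of patients below the low-zinc cutoff. A population that mixes two such groups varies a good deal even if patients within each group are nearly alike. An unadjusted comparison in such a mix carries all of that variation.

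If the SD is too small, the 80% is too high, and the trial may well miss a real 3-day benefit. That matters for how the result is read. The Limitation paragraph under Statistical analysis already says that finding no benefit would mean low zinc is a consequence of inflammation. An underpowered comparison cannot carry that conclusion.

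**Working it through.** **Inputs.** From the sample-size paragraph: 60 randomised 1:1, 10% dropout, alpha 0.05, difference 3 days, SD 4 days. Evaluable per arm: 30 × 0.9 = 27. Two-sided testing is my assumption. From the Preliminary Results: low-zinc share p = 0.23, recovery 25 and 8 days, gap 17 days.

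**Step 1: reproduce the plan's figure.** With the normal approximation, power = Φ(3 / (SD × √(2/27)) − 1.96), and √(2/27) = 0.272.
- SD 4: 3 / 1.089 = 2.756; Φ(0.796) = 78.7%. The t-test gives 77.2%.
- With no dropout (30 per arm): 82.8% (normal) or 81.5% (t).

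The stated 80% follows from the plan's own inputs to within rounding and choice of approximation.

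**Step 2: smallest overall SD if 25 and 8 are means.** Suppose the control group is the other 77%. With no spread at all within groups, the between-group part alone is

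17 × √(0.23 × 0.77) = 17 × 0.421 = 7.15 days.

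**Step 3: smallest overall SD if they are medians.** At least half of the control group (0.385 of all patients) is at or below 8 days, and at least half of the low-zinc group (0.115) is at or above 25. The variance is smallest when those patients sit exactly on 8 and 25 and the remaining half sit at the overall mean:
- mean = (0.385 × 8 + 0.115 × 25) / 0.5 = 11.91
- variance = 0.385 × 3.91² + 0.115 × 13.09² = 5.89 + 19.71 = 25.59
- SD = 5.06 days

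Real data, not piled on three values, would spread more than this.

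**Step 4: power and detectable difference with 27 per arm.** The difference detectable with 80% power is (1.96 + 0.842) × 0.272 × SD = 0.762 × SD.

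| SD (days) | Power for 3 days, normal | Power, t-test | Detectable at 80%, normal |
|---|---|---|---|
| 4 (plan) | 78.7% | 77.2% | 3.05 days |
| 5.06 (floor, medians) | 58.7% | 57.1% | 3.9 days |
| 7.15 (floor, means) | 33.8% | 32.7% | 5.5 days |

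Because the last two SDs are minima, their powers are ceilings. With 30 per arm and no dropout the ceilings are 62–63% and 36–37%. A one-sided test (1.645 in place of 1.96) gives Φ(2.179 − 1.645) = 70% and Φ(1.541 − 1.645) = 46%.

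**Step 5: dependence on the zinc mix.** The floor is 17 × √(p(1 − p)) for means and 17 × √(p(1 − p)/2) for medians.

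| Low-zinc share | Floor, means | Floor, medians |
|---|---|---|
| 10% | 5.1 | 3.6 |
| 15% | 6.1 | 4.3 |
| 23% | 7.15 | 5.06 |

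The floor passes 4 days at a share of about 6% (means) or 13% (medians).

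**The case against.** The strongest reply is that the cohort figures do not determine the trial's SD.

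- **Means or medians.** The text does not say. The 7-day floor needs means; under medians it is 5 days. This stands, and both must be carried.
- **Who the control group is.** The Preliminary Results never say that it is everyone else, or that the recovery comparison used the 50 µg/dl cutoff. The 23/77 split is an inference.
- **Trial population.** The trial excludes patients expected to live less than 72 hours and those who cannot take oral medication, and it drops patients without primary endpoint data. If deaths are removed using the cohort's 21% and 5% mortality, the low-zinc share becomes 0.23 × 0.79 / (0.23 × 0.79 + 0.77 × 0.95) = 0.182 / 0.913 = 19.9%. The means floor is then 17 × √(0.199 × 0.801) = 6.8 days and power about 37%. This assumes the cohort figures included the deaths. The bound moves, but not enough to restore 80%.
- **Recovery definition.** The composite in Task 1.1.2 may differ from the cohort's undefined time to recover, and follow-up ends at Day 28. Either could narrow the spread.
- **Low-zinc patients only, or adjustment.** The Preliminary Results speak of supplementing low-zinc patients. If only they were enrolled, or if the analysis adjusted for baseline zinc, the between-group part would drop out and the conflict would not follow. The listed criteria and the analysis section provide for neither.
- **Equal SDs.** The calculation keeps one SD for both arms, as the plan does. A benefit concentrated in low-zinc patients would narrow the supplemented arm and raise the ceilings.

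These points make the size conditional. None of them supplies a source for the 4 days.

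**Conclusion.** The SD of 4 days is unsupported and, on the natural reading of the sponsor's own cohort, too small. If the trial's zinc mix resembles the cohort, the control group is the remaining 77%, recovery is measured comparably and the SD is the same in both arms, the overall SD is at least about 7 days (means) or 5 days (medians). Power for a 3-day difference is then at most about 34% or 59%. Neither reading supports 80%. A lower low-zinc share or a different recovery definition would change these bounds.

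A reader might infer three stronger things that the documents do not support:
- That the SD is at least 7 days without condition. That requires means, which the text does not state.
- That power lies between 26% and 34%. The lower end comes from adding an assumed within-group SD of 4 (√(7.15² + 4²) = 8.2 days, 26–27%). That 4 is not a cohort figure, so the range bounds nothing from below, and under medians power could be higher than 34%.
- That the sponsor miscalculated. The formula returns 77–79% from the plan's inputs; the weakness is the input.

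**What to change.** 1. Compute the SD of time to recovery from the existing 249-patient dataset, applying the trial's definition of clinical recovery and its eligibility criteria. State the result, its source, and whether the 25 and 8 days are means or medians.
2. With that SD, restate in the sample-size paragraph the power for a 3-day difference and the difference detectable with 80% power, both for 27 evaluable patients per arm. State the sidedness.
3. Pre-specify adjustment of the recovery analysis for baseline serum zinc, already measured at Visit 1. Quote power for that analysis using the residual SD after adjustment, also estimated from the cohort. If the residual SD proved to be about 4 days, power would be back near 77–79%, so an unadjusted figure would misdescribe the adjusted analysis.

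The sponsor should not write 7–8 days or 26–34% into the protocol. That would replace one unsupported SD with another.

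The cost is one calculation on data already held, a rewritten sentence and one pre-specified covariate. No additional patients or measurements are needed to correct the statement. The downside is that the stated power will probably become less favourable.
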